13.1 Laboratory trial

In preliminary laboratory clinical trials in London, 17 participants will test all products that have been found to exhibit repellency to *Musca sorbens* in benchmarking laboratory studies. These will be chosen from: DEET (N,N-diethyl-3-methylbenzamide), IR3535 (3-[N-butyl-N-acetyl]-aminopropionic acid ethyl ester), Picaridin (2-(2-hydroxyethyl)-1-piperidinecarboxylic acid 1-methylpropyl ester); PMD (para-Menthane-3,8-diol) or permethrin (m-Phenoxybenzyl)-cis,trans-3-(2,2-dichlorovinyl)-2,2-dimethylcyclopropanecarboxylate). Products tested will be either (1) topical repellents, or (2) in long-lasting, plastic formulations of repellents that can be worn on the body (wearable repellent technologies). The insect repellent synergist Vanillin (4-Hydroxy-3-methoxybenzaldehyde) may be added to the long-lasting plastic formulations, to improve the duration of protection.

As all participants will test all products and all concentrations, this study is non-randomised. The combination of product and product format to be tested will be determined before the study commences. Participants will be asked to place their arm in a cage with 100 *Musca sorbens* flies, and the behaviour of the flies on the surface of the arm and hand will be filmed for ten minutes. This modified arm-in-cage assay has been developed specifically for use with *Musca sorbens*.

There will be a two-stage selection process to determine which repellent products, at which concentration (dose), should be carried forward to the field trial. In the first stage, a single measure of Protective Efficacy (PE) will be used to determine protection, by measuring the duration of fly-arm contact after application of a repellent product (test measurement) relative to that before application of the product (control measurement). By only selecting repellent products/concentrations that protect against at least 30 % of fly contact immediately following application (at time zero), those with little or no effect will be disregarded.

In the second stage and using the same participants, those repellent products/concentrations that demonstrated at least 30 % PE will be measured for the persistence of effect, over a six-hour period. For the wearable repellent devices, tests will further be repeated at one, two, three and four weeks later. The duration of fly contact in a modified arm-in-cage assay will again be used. This stage will allow estimations of persistence including the Median Effective Dose (ED_{50}), the Median Effective Time (ET_{50}) and the Complete Protection Time. Estimations of persistence will allow final selection of repellent products/concentrations to be tested in the field trials.

13.2 Field trial

In the field clinical trial, eligible participants will be randomised between groups (study arms), each of which will test only one topical repellent or slow-release wearable repellent device, at one concentration. A maximum of four groups will be tested in addition to a control group, and each group will contain 29 children between the ages of three and 12 years. The additional control group, receiving no product, will allow for temporal comparison of fly contact across a day of testing.

The combination of product and product format to be tested will be determined before the study commences. The PE will be determined by measuring the frequency of fly-eye, fly-nose, fly-mouth and fly-face contacts by *Musca sorbens* after application of the product, in a 'field' environment where these flies are naturally present at high density. Control measurements will be taken of fly contact on each participant prior to this. Test measures will be repeated over a period of six hours to determine the ET_{50} , and for wearable repellent devices, participants will continue to wear the

product and tests will be repeated at one, two, three and four weeks later. Topical repellents will be applied by the Stronger-SAFE field team nurses, who will also demonstrate how to wear the repellent devices. A qualitative assessment of acceptability and barriers to use will be carried out at the end of the trial.

14 Study setting and populations

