12.2 Secondary Objectives

1. To compare the duration of protection offered by different repellent products using the median Complete Protection Time (mCPT)
2. To compare the effectiveness of protection offered by different repellent products using the median effective dose and median effective time
3. To assess the acceptability of the repellent products tested in the field trials using qualitative data from participants.

13 Trial Design

This is a within-subject, non-masked, trial of the use of commercially available insect repellents against *Musca sorbens*, with two consecutive participant groups in the laboratory and in the field, and a primary endpoint of measuring the protective efficacy of each repellent product.

The trial is within-subject to allow comparison of *M. sorbens* contacts on the same participants both before (control) and after (test) application of the repellent or repellent device. This is to mitigate any possible inter-individual attractiveness effects. Control sampling will be conducted before test sampling, to preclude contamination of the control sampling by the test sampling. For this reason, the trial is not masked.

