21.2.3 Topical repellents

Eligible **participants** will be randomly allocated in equal proportions to the study groups, as per section 13. The repellent products and product formulations to be tested will be determined before the study commences. Each study participant will test only one product type, to minimise participant discomfort. Participants will be advised not to apply any cosmetics associated with a strong scent, such as perfume, hand cream, body wash, or other scented products. Additionally, volunteers will be asked not to consume spicy foods, i.e. curries, chillies and garlic for the 12 hours prior to the tests. This will be verified with the participants prior to the commencement of any tests.

The participants face will first be washed with unscented soap then rinsed with water and towel dried. The participant will then be seated comfortably on a chair outside their house, facing the investigators (entomological field worker and nurse), and will be instructed to refrain from touching the face or brushing away landing flies. For the first test, the diluent alone (50 µL) will be tested as a control. This will be applied to the participant's face (cheeks) and allowed to dry for one minute. The participant's face will then be videoed for ten minutes by the investigator or field laboratory assistant. During this time period, fly behaviour will be manually recorded and scored. The video footage will retrospectively be analysed for (i) fly-eye (ii) fly-nose (iii) fly-mouth and (iv) fly-face contact. After this ten-minute period of control measurements, the pre-allocated topical repellent will be applied to a circular area on the participant's cheek by the Stronger-SAFE field

team nurses. Topical repellents will be applied in a 6 cm diameter circle on the cheek, at least 3 cm below the eye and positioned away from the nose and mouth. The repellent will be allowed to dry for one minute, then the videoing and observation will be repeated for another ten-minute period. Test measurements will then be repeated hourly for five further time points (Figure 7). After the final time point, the participant will be provided with soap and water to clean off the topical repellent.

[figure not shown]

Figure 7. Study design for estimation of personal protection by topical repellents from fly-eye and fly-face contacts by *Musca sorbens*. This process will be repeated for each of 29 participants.

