21.2.4 Wearable repellent devices

Control measurements will be taken for a ten-minute period, exactly as with the topical repellent testing, but omitting the face washing step. After this, the pre-allocated wearable repellent device will immediately be administered. Field nurses will demonstrate how to wear the repellent device, which will then be given to the participant to wear, or his/her primary caregiver to put on to the participant. The participant will then be seated again, and the videoing and observation repeated for another ten-minute period, as with the topical repellent testing. Again, the ten-minute observation period will then be repeated hourly for five further time points. After the six-hour test period, the participant will be asked to continue to wear the repellent device. The investigators will return one week later to repeat test sampling, at which point they will measure for ten minutes with the wearable repellent device still in place, then remove the device and measure for a further (control) ten minutes (Figure 8).

[figure not shown]

Figure 8. Study design for estimation of personal protection by wearable repellent devices from fly-eye contacts by *Musca sorbens*. This process will be repeated for each of 29 participants.

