22.4.2 Field trials

The participant's face will be observed and filmed for ten-minute periods. During this time, the participant will be required to sit motionless and allow flies to crawl freely over their face and around their eyes, nose and mouth. In this study setting this burden would be considered 'the norm', with children rarely bothering to brush away flies due to their extreme persistence and prevalence.

At the first time-point of testing, the child will be asked to sit for ten minutes of control measurements, immediately followed by ten minutes of test measurements, with the application of insect repellent in-between. Ten-minute duration follow-up sessions will be conducted hourly for the rest of the day (six hours). As participants may be as young as three years old, sitting motionless for these periods may be difficult, additionally, the child may become distressed.

We will encourage the children to conform to protocol as far as possible but will make reasonable judgement around levels of distress. To be, and remain, eligible for the field trial, we state "15. The participant does not become unacceptably upset during the procedures". The same methodology 'Fly-eye studies' are currently underway as part of the Stronger-SAFE Phase 1 study of Ct transmission in the same study site. In Phase 1, the team are conducting 'Fly-eye studies' on two children in each of more than 200 households, and as such have gained a great amount of experience in this type of work. The Phase 1 'Fly-eye studies' constitute two components, the ten-minute observation/videoing period as described above in this protocol, followed by 15 minutes of catching flies from the child's face. So far, we have not observed many instances in which the child becomes upset in the initial ten-minute period, with the latter fly-catching exercise generally proving more difficult. In instances where the child does become upset, the field team tries to calm the child with the help of the primary caregiver, or his/her friends and family, and encourage them to allow work to continue. If the child continues to be upset, sampling/participation is

discontinued for that child. In terms of managing distress, the same protocol will be followed for this study.

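### Field children are allocated before the day-0 control reading, so C is measured with the arm already fixed in an open trial; opening the allocation after that reading is a cheap improvement for day 0 only.

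*Combined protocol and SAP*

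**What the plan says.** Section 13.2 states: "In the field clinical trial, eligible participants will be randomised between groups (study arms), each of which will test only one topical repellent". That sentence does not fix the order of allocation and control reading. The order comes from the procedures. For topical products, section 21.2.3 says: "After this ten-minute period of control measurements, the pre-allocated topical repellent will be applied to a circular area". For wearables, section 21.2.4 says: "After this, the pre-allocated wearable repellent device will immediately be administered". In both, the product is already assigned when the control period closes.

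Section 13 gives the sequence of readings and treats it as the reason for not masking: "Control sampling will be conducted before test sampling, to preclude contamination of the control sampling by the test sampling". Section 26.3.1 makes C, the contact frequency before the product, the denominator of PE. Section 21.2.3 has contacts scored by hand during the reading, with the film analysed afterwards.

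The control preparation depends on the product format. In the topical procedure the face is washed and the diluent "will be tested as a control. This will be applied to the participant". In the wearable procedure the control is taken "exactly as with the topical repellent testing, but omitting the face washing step". Section 21.2 does not describe the preparation of the no-product group.

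On distress, section 15.2 makes not becoming unacceptably upset during the procedures an eligibility criterion. Section 22.4.2 then says: "If the child continues to be upset, sampling/participation is" discontinued for that child. The same section reports that few children became upset in the first ten minutes of similar fly-eye work.

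**The concern.** The control reading always comes first, so the arm need not be known while it is taken. The plan sets the arm earlier, and this has two consequences.

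First, the people who seat the child, run the reading and score contacts can know whether a product or nothing will follow. Any effect of that knowledge on C passes straight into PE, and the field comparison in section 19.2 is product against no product. The plan describes neither allocation concealment nor scoring of the film without knowledge of the arm. Section 35's counterpart in the text, 16.2.2, says the field PE informs which repellents enter the Phase 3 trial.

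Second, a criterion that can be judged only once procedures begin is applied after randomisation. A child as young as three who cannot sit through the control reading has used an allocated place and yields no C, hence no PE. Allocating later would turn that child into a screening failure who can be replaced.

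**Working it through.** **Order of events.** Set side by side, 13.2 (eligible children are randomised), 21.2.3 and 21.2.4 (product pre-allocated when the control period ends) and 13 (control before test) give: eligibility, allocation, day-0 control reading, product, test readings.

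**The plan's own sample size.** Inputs from section 19.2: difference 30 points, SD 30, power 90%, 25% loss. Two-sided 5% is an assumption, since no alpha is stated.
- Standardised difference d = 30/30 = 1. The two-sample t calculation gives 22.02 per arm, rounded up to 23, which matches the plan.
- 23 × 1.25 = 28.75, rounded up to 29, which also matches.
- Applying 25% loss to 29 leaves 29 × 0.75 = 21.75 per arm, with power 89.6%. This is slightly under 90% because of how the loss was added, which is a separate matter.

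**Loss at the control reading.** Let f be the share of randomised children who cannot complete it. The documents give no value, so f = 5% to 20% is an assumed range. Two cases are shown: this is the only loss, n = 29 × (1 − f); or the full 25% is lost afterwards as well, n = 29 × (1 − f) × 0.75.

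| f | n, only loss | power | n, plus 25% | power |
|---|---|---|---|---|
| 0% | 29.0 | 96.3% | 21.8 | 89.6% |
| 5% | 27.6 | 95.4% | 20.7 | 88.0% |
| 10% | 26.1 | 94.3% | 19.6 | 86.1% |
| 15% | 24.7 | 93.0% | 18.5 | 84.0% |
| 20% | 23.2 | 91.5% | 17.4 | 81.7% |

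With allocation after the reading, 29 are randomised per arm whatever f is, so the f = 0 row applies throughout. Five arms of 29 make 145 children. The number who must enter the reading is 145/(1 − f): 153 at 5% and 162 at 10%.

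**Bias in C, as a hypothetical only.** If C were over-counted by a fraction b in product arms alone, the observed PE would be 1 − (1 − p)/(1 + b), where p is the true PE. For b = 5% or 10%, a useless product shows 4.8 or 9.1 points, and a true 30% reads 33.3% or 36.4%. At 23 per arm with SD 30, the false-positive rate would be about 8% or 17% instead of 5%. The values of b are invented to show how the error carries through; nothing in the documents supports them.

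**What later allocation cannot reach.** At the one-week wearable visit the team will "then remove the device and measure for a further (control) ten minutes", necessarily with the arm known. The test count T is taken after allocation at every time point. Distress after the control reading remains a post-randomisation loss.

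**The case against.** The strongest reply is that little is at stake.

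A reader might infer that the field trial has a pass mark which children fail at the control reading. It does not: the five-contact minimum in section 21.1.3.1 is for the laboratory only. The route shown here is distress, and section 22.4.2 says this was uncommon in the first ten minutes, from work with two children in each of more than 200 households. This stands.

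A reader might infer that power falls to 82% to 88%. That follows only if control-reading losses are added to the whole 25% allowance, which section 15.4 explains by the difficulty of finding children at home over a month. Topical arms finish in one day. These losses also precede any product, and nothing in the documents suggests that they differ by arm. This stands.

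A reader might infer that type I error is inflated. The documents give no size for any over-count and no rule for accepting or repeating a field reading. The face is filmed throughout, and section 26.1.2 requires trained observers who follow standard procedures. The exposure exists, but its size is unknown.

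A reader might also infer that later allocation removes both problems. It does not, because T, the later wearable controls and later distress are untouched.

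Finally, because preparation differs by format, the arm cannot simply be hidden under the present procedures. Allocating format first and product versus no product afterwards would split the single no-product arm. With an even split, 23 against 11.5 evaluable gives about 77% power. This also stands, and it limits the fix to a common preparation.

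None of this answers the point about order: C is taken with the arm fixed when it need not be.

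**Conclusion.** The point holds in a limited form, and is best labelled a cheap improvement. The text shows that the arm is fixed before the day-0 control reading in a non-masked trial. It also shows that a child stopped for distress during that reading is lost after randomisation without a PE. The size is not known. The loss is probably small: as the only loss, even 20% would leave power at about 91%. The power figures rest on the section 19.2 inputs, an assumed two-sided 5% and an assumed f. They and the type I error figures are illustrations, not expected effects. The reason to act is that the change is simple and the order cannot be repaired once data are collected. Nothing in the text blocks it, since section 15.2 has every child agree to skin testing for all the trial's repellents before the trial.

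**What to change.** In sections 13.2, 20.2, 21.2.3 and 21.2.4:

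1. Define one preparation for the day-0 control reading in all arms, including the no-product arm. Sections 21.2.3 and 21.2.4 differ on face washing and must be reconciled.
2. Complete the control reading and lock it in ODK, which section 26.2 says already captures data at collection with an audit trail.
3. Only then open the next concealed allocation.
4. State that a child who cannot complete the control reading is not randomised and is replaced.
5. State that this protects the day-0 C only.

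Do not allocate format first, because that divides the single no-product group.

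Cost: a short protocol change and a field procedure step. Teams carry all field products to each house. About 153 to 162 children enter the reading instead of 145 if 5% to 10% cannot complete it. The control preparation for wearables is likely to change slightly.

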14.1 Age of participants

This clinical trial has two consecutive participant groups, firstly adults in the laboratory trials and then children of age three to 12 years in the field trials. The first study will test proof-of-concept for the use of insect repellents against *Musca sorbens*, will narrow down repellent candidates, and will not replicate a naturalistic setting. The second study will take place in a trachoma-endemic setting, where *Musca sorbens* are prevalent and likely contributing to disease transmission. Because fly harassment around the eyes, nose and mouth is not a problem that adults experience, it would neither be possible nor naturalistic to conduct the field study using adults.

14.2 Laboratory trial (London School of Hygiene & Tropical Medicine)

Laboratory studies will be conducted in specialised, Good Laboratory Practice (GLP)-accredited insect testing facilities at LSHTM. A colony of field-collected, but laboratory-reared, *Musca sorbens* are maintained by the lead investigator in insectary facilities at LSHTM, these will be used for all laboratory trials. We will enrol adults (>18 years) of both sexes, among staff and students of LSHTM, to this component of the trial.

14.3 Field trial (Oromia, Ethiopia)

Field studies will be carried out in one woreda (district) in the West Arsi Zone of Oromia, Ethiopia, in the same approximate locality that the other Stronger-SAFE Phase II studies are being conducted, but in villages (kebeles) that have not previously been enrolled to any other Stronger-SAFE study component. Kebeles will be chosen where TF prevalence is believed to be low (TF1-9<40%). We will perform trachoma screening in the selected kebeles to confirm TF prevalence. We will select low prevalence areas as these studies do not incorporate clinical or Ct prevalence outcomes, requiring only fly populations, therefore we will aim to set the study site where there is minimal disease transmission but a high abundance of *Musca sorbens*. We will conduct a preliminary assessment of the suitability of study sites by visiting and observing the extent of local fly-eye nuisance among children. We will enrol households with children aged three to 12 years, as they are at increased risk of TF relative to adults, and also tend to experience higher levels of face fly nuisance. This field study location will provide an excellent context for informing on the wider applicability of the study results, due to both the very high TF prevalence rates (21) and fly population densities (29) experienced in this area. Small-scale field repellency trials will be conducted at the participant's houses.

15 Trial eligibility and withdrawal criteria

Participants will be healthy individuals, and will be included in the study if they meet all of the following criteria:

15.1 Laboratory trial eligibility criteria

1. Participant is aged 18 years and ≤ 65 years and in good health
2. Participant has a good understanding of the procedures of the study and agrees to abide to these procedures
3. Participant is able to communicate well with the investigator, and attend the laboratory for all aspects of the laboratory studies
4. Participant has no known adverse reactions, or evidence at screening of adverse reactions, to the commercially available repellents DEET, PMD, IR3535, Picaridin or Permethrin, or to Vanilla
5. Participant has no known history of skin allergies or hypersensitivity to topical creams
6. Participant agrees to a pre-trial skin reactivity test for all the repellents that will be used in the trial
7. If in the event of the participant experiencing an adverse reaction to a repellent during the trial, the participant agrees to inform his/her general practitioner and seek appropriate treatment if necessary
8. Participant is willing to allow laboratory-reared *Musca sorbens* flies to land and crawl on their arm, during the modified arm-in-cage assay, for periods of up to ten minutes at a time
9. Participant agrees not to use any perfumed or scented product, including bathing products, for a 24-hour period before each laboratory session
10. Participant has signed informed consent
11. Participant is not a smoker, and will agree to refraining from smoking for the 12 hours before each laboratory trial

